1. SUMMARY

In the U.S. the number of obese women entering pregnancy has more than doubled in the past 30 years. Pregavid obesity alone however is not the only cause for concern since two-thirds of obese women gain weight in excess of the 2009 IOM gestational weight gain recommendations and attempts to manage gestational weight gain to date have failed. To improve weight management of obese pregnant women, there is a critical need to deliver specific, evidence-based recommendations on energy intake and energy expenditure (physical activity); the two primary determinants of weight gain in non-pregnant individuals. We will evaluate energy intake and energy expenditure during pregnancy (13 to 37 weeks) and through 12 months postpartum in at least 60 obese women. We will test the hypothesis that obese pregnant women with weight gain above the IOM guidelines, 'High Gainers', will have increased energy intake but no evidence for changes in energy expenditure after adjustment for the weight gained when compared to women with appropriate gestational weight gain, 'Normal Gainers'. The primary outcome variables are 1) energy intake during pregnancy and 12 months postpartum measured with the energy balance method and with a mathematical model of maternal energy intake and 2) the free-living energy expenditure and sleeping metabolic rate (absolute and adjusted for maternal body composition and fetal size) during pregnancy. Secondary outcomes include measurement of changes in physical activity and substrate oxidation, determinants of energy intake including fasting concentrations of leptin, total ghrelin, peptide YY, cholecystokinin and determinants of energy expenditure including urinary epinephrine and norepinephrine, and fasting concentrations of T3, T4 and TSH.

2. BACKGROUND AND SIGNIFICANCE

2.1. Definition and prevalence

Currently in the United States, 31.9% of reproductive age women (20-39 years) are estimated to be obese [1] and 8% severely obese [2]. Obesity at conception as well as excess gestational weight gain leads to adverse health outcomes for the mother [3-6] and more alarming, the infant [6-9] that are sustained for decades later.

In an attempt to counteract these trends, the Institute of Medicine (IOM) performed a detailed review of observational data in pregnant women and infants, and defined, within each BMI classification, boundaries for appropriate weight gain during pregnancy [10]. According to the IOM, gestational weight gain in obese women should be limited to 5-9 kg [10]. To be compliant with the gestational weight gain guidelines, the IOM suggests pregnant women receive dietary advice and physical activity counseling throughout pregnancy. Despite these recommendations, recent data in 227,149 obese pregnant women indicate that more than 55% of obese women in the U.S. exceed the IOM guidelines for gestational weight gain [11]. Furthermore, to date, lifestyle interventions specifically designed to attenuate weight gain in obese pregnant women have failed [12-17]. In order to improve weight management in obese pregnant women, there is a critical need to understand the determinants of gestational weight gain. In support of this contention, the IOM recognized that, "there remains a lack of information to relate dietary intake or physical activity to gestational weight gain even though they are primary determinants of weight gain in non-pregnant individuals" [10].

There is little knowledge of the determinants of gestational weight gain in pregnant women and no studies have been conducted specifically in pregnant women who are obese. Successful weight management programs in non-pregnant individuals rely on individualized prescriptions of energy intake and physical activity [18-21]. Understanding how changes in energy intake, energy expenditure and physical activity during pregnancy contribute to gestational weight gain is critical for designing effective interventions for pregnant women. To advance the management of gestational weight gain in obese pregnant women, studies are thereby needed to: 1) understand the simultaneous changes in energy intake, energy expenditure and physical activity throughout pregnancy and, 2) evaluate these measures in relation to gestational weight gain and the 2009 IOM guidelines for weight gain during pregnancy.

Objective assessments of energy intake can be derived from the energy balance method by summing total daily energy expenditure and changes in body energy stores. We have shown that the energy balance method can be

used to estimate energy intake during weight loss with good accuracy and precision [22, 23] and have preliminary data validating this method during weight gain. Objective assessments of energy intake have not been undertaken in obese pregnant women and almost no data exist. Using data from a landmark study that collected simultaneous measurements of body composition (by the 4-compartment model) and energy expenditure by the doubly labeled water technique [24], we computed energy intake in the 3rd trimester by the energy balance method. In overweight women with gestational weight gain above the 2009 IOM guidelines ('High Gainers'), energy intake in the third trimester was 3503 ± 666 kcal/d compared to 2617 ± 400 kcal/d for women with appropriate gestational weight gain ('Normal Gainers'). As expected, energy expenditure in these women increased in proportion to gestational weight gain. When the change in energy expenditure was adjusted for change in maternal body weight and body composition (mother plus fetus), energy expenditure was higher than expected but not different between 'High Gainers' and 'Normal Gainers'. These preliminary data indicate that a large energy intake and not an impaired increase in the energy expenditure underlie excess gestational weight gain in 'High Gainers'.

2.2. Specific aims and hypotheses

The aim of this study is to test the hypothesis that obese pregnant women with weight gain above the IOM guidelines, 'High Gainers', will have increased energy intake but no evidence for changes in energy expenditure after adjustment for the weight gained when compared to women with appropriate gestational weight gain, 'Normal Gainers' (Figure 1).

Aim 1: Measure energy intake in obese women during pregnancy. The primary outcome is energy intake over the last 2 trimesters of pregnancy measured by: 1) the energy balance method (using doubly labeled water and change in maternal energy stores by whole-body MRI and fetus size by 3-D ultrasound) and, 2) our energy balance model of gestational weight gain and energy intake.

Hypothesis 1: Energy intake will be significantly larger in 'High Gainers' versus 'Normal Gainers'.

Aim 2: Measure total energy expenditure in obese women during pregnancy. We will combine the most accurate and precise methods to assess sedentary (sleeping metabolic rate in a room calorimeter) and free-living (doubly labeled water) energy expenditure, and physical activity.

[figure not shown]
Hypothesis 2: Absolute energy expenditure (unadjusted) during pregnancy will increase proportionally to increase in metabolic mass (mother plus fetus) whereas energy expenditure adjusted for maternal body energy stores and fetus size will not differ between 'High Gainers' and 'Normal Gainers'.

Aim 3: Measure energy intake and energy expenditure in obese women 12 months postpartum and their relationships to "postpartum weight loss".

Hypothesis 3: The percentage of weight normalization (postpartum weight loss as a percentage of gestational weight gain) will be proportional to the decreased energy intake from late pregnancy to 12 months postpartum.

3. RESEARCH DESIGN

This is a single arm, prospective study. In this study, we will enroll up to 75 obese, pregnant women to complete at least 60. This study will be performed at Pennington Biomedical Research Center in Baton Rouge, Louisiana. Study outcomes will be assessed at three time points during pregnancy; namely, gestational weeks 13-16 (early), 24-27 (mid), and 35-37 (late); and at two time points postpartum; namely, postpartum weeks 22-25 and 48-56 (postpartum testing). Infants born to the mothers enrolled in the MomEE study will complete 1 study visit before 10 days of life to measure anthropometrics, body composition measurements, and questionnaires.

3.1. Primary outcomes

The primary outcome variables are 1) energy intake during pregnancy and 12 months postpartum measured with the energy balance method and with a mathematical model of maternal energy intake, and 2) the free-living energy expenditure and sleeping metabolic rate (absolute and adjusted for maternal body composition and fetal size) during pregnancy.

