10. DATA MANAGEMENT

10.1. Statistical power and sample size

The primary outcome is energy intake during pregnancy. We were able to apply the energy-balance model to

Table 4. Minimum sample size for power at .80 and .90, ratio between groups 1:2

Standard Deviation kcal/d	Mean Difference kcal/d	Power (β)	Group 1 N	Group 2 N
700	541	.90	27	54
700	468	.80	27	54
700	600	.90	22	44
700	520	.80	22	44
700	688	.90	17	34
700	590	.80	17	34

estimate energy intake in previously reported data on energy requirements during pregnancy [82]. The standard deviation of energy intake in the third trimester was conservatively estimated to be 700 kcal/d using Butte’s data on total energy expenditure and energy deposition of fat mass and fat-free mass.

We hypothesize that women who will exceed 2009 IOM recommendations for weight gain during pregnancy, the ‘High Gainers’, will have a larger energy intake than those who will keep their weight gain within IOM guidelines, the ‘Normal Gainers’. Because of the intervention, we predict to have a decrease in the incidence of ‘High Gainers’ from 66% to a rate below 50%. Therefore we predict that the ratio “High Gainers” to “Normal Gainers” will likely be 1:2. Our power/sample size analysis (Table 2) assumed: 1) power ≥ 0.90 , 2) alpha = 0.05, 3) the null hypothesis will be tested against a two-directional alternative, 4) the common standard deviation for energy intake is 700 kcal/d and 5) conservative estimates that the ratio between the two groups, ‘High Gainers’ to ‘Normal Gainers’ is 1:2.

As shown in Table 2, with subject assignment to the 2009 IOM guidelines being 1:2, we require a minimum of 51 subjects, to detect a between group difference of 590 kcal/d with 90% power or 520 kcal/d with 80% power. To allow for early deliveries, the inability to perform MRI in some subjects late pregnancy, due to limitations with the field of view, and that 10% of subjects will gain less weight than recommended; we aim to complete at least 60 subjects.

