10.2. Data analysis plan

Analyses will be performed in SAS version 9.3 (SAS Institute, Cary, NC). Statistical significance will be set at $p \leq 0.05$.

Aim 1: Mixed models will be used to analyze differences between 'High Gainers' and 'Normal Gainers' with respect to energy intake during pregnancy estimated with the energy balance method. Adjustments for covariates, such as maternal age, fetal size and parity will be made if appropriate. Least square means will be compared with the mixed models contrasts. Energy intake from the energy balance model will be analyzed analogously in the context of repeated measurements. We expect that energy intake by the two methods will all be significantly higher in 'High Gainers' versus 'Normal Gainers'. In addition, the two methods for measuring energy intake will be cross validated with each other and compared with Bland-Altman analysis. Regression analyses will be used to assess the relationship between energy intake during pregnancy and postpartum weight loss after 1 year. We predict that lower energy intake during pregnancy is associated with better postpartum weight loss results after 1 year.

Aim 2: Analysis of covariance will be used to assess significance of differential changes ('High Gainers' versus 'Normal Gainers') in absolute energy expenditure. Differential changes in energy expenditure after adjustment for changes in maternal and fetal size will be tested analogously. For secondary hypotheses, change in energy expenditure attributable to accelerometer-measured physical activity (steps per min) will be analyzed to investigate its role in differential energy balance in 'High Gainers' versus 'Normal Gainers'.

Analyses of exploratory aims: The change in determinants of energy intake and energy expenditure in blood and urine from early to late pregnancy and 12 months postpartum will be analyzed by repeated measures with IOM classification and time interactions. Adjustments for covariates, such as maternal age, fetal size, parity and early pregnancy values will be made if appropriate. To control for type I error, statistical significance for all multiple comparisons will be adjusted using the Tukey-Kramer method.

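### The plan gives three different accounts of what is primary and no rule across them, so a positive primary claim could rest on any of up to four tests, each at 0.05

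*Combined protocol and SAP*

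**What the plan says.** Three parts of the plan define the primary outcome differently.

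- Section 3.1, repeated in the Summary (section 1), lists several: "The primary outcome variables are 1) energy intake during pregnancy and 12 months postpartum measured with the energy balance method". A model-based estimate is added for the same two periods. The list then turns to expenditure: "the free-living energy expenditure and sleeping metabolic rate (absolute and adjusted for maternal body composition and fetal size) during pregnancy". Intake at two periods by two methods is four variables. Two expenditure measures in two forms are four more, so eight in all.
- Section 2.2, Aim 1, is narrower: "The primary outcome is energy intake over the last 2 trimesters of pregnancy measured by" two methods, the energy balance method and the investigators' model.
- Section 10.1 is narrower again: "The primary outcome is energy intake during pregnancy". Its sample size covers this outcome only, with "2) alpha = 0.05, 3) the null hypothesis will be tested against a two-directional alternative".

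On testing, section 10.2 says: "Statistical significance will be set at" p ≤ 0.05. It gives no testing order, no division of alpha and no requirement that both intake methods succeed. It does say that both are expected to be significant. The one sentence on type I error, a Tukey-Kramer adjustment, closes the paragraph on exploratory aims.

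**The concern.** A reader cannot tell from the plan which result decides the study. If intake by the energy balance method were not significant, a significant result for model-based intake, total daily energy expenditure (TDEE) or sleeping metabolic rate (SMR) could still be presented as a primary finding at the nominal 5%, and section 3.1 would support that label. The choice could be made after the data are seen.

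The Tukey-Kramer sentence does not close the gap, even if it is read as reaching beyond its own paragraph. That method adjusts comparisons among group means within one outcome. The primary analysis has only two groups, because Low Gainers are excluded (section 8.11). The multiplicity here lies across outcomes.

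**Working it through.** **1. The plan's own figure.** Inputs from section 10.1: SD 700 kcal/d, two-sided alpha 0.05, groups of 17 and 34, difference 590 kcal/d, power 0.80 (Table 4, last row).

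- Standard error = 700 × √(1/17 + 1/34) = 207.9.
- Standardised difference = 590 / 207.9 = 2.84.
- Power = Φ(2.84 − 1.96) = 81% by the normal formula and 79% by the t test.

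The other five rows of Table 4 also reproduce. The power calculation therefore spends the whole 0.05 on one comparison. (The sentence below the table pairs 590 kcal/d with 90% power and 520 kcal/d with 80% for 51 women, which Table 4 does not give. That is a separate matter and does not affect this point.)

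**2. Which of the eight can produce a positive claim.**

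| Variable called primary in 3.1 | Planned High versus Normal comparison in 10.2? | Would a difference fit the hypotheses? |
|---|---|---|
| Pregnancy intake, energy balance method | Yes (Aim 1) | Yes |
| Pregnancy intake, model | Yes (Aim 1) | Yes |
| Absolute TDEE | Yes (Aim 2) | Could be reported so |
| Absolute SMR | Yes (Aim 2) | Could be reported so |
| Adjusted TDEE | Yes (Aim 2) | No: Hypothesis 2 predicts no difference |
| Adjusted SMR | Yes (Aim 2) | No: Hypothesis 2 predicts no difference |
| 12-month intake, energy balance method | No | Not applicable |
| 12-month intake, model | No | Not applicable |

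For the expenditure rows, section 8.14 says that each component is analysed in absolute and adjusted form. For 12-month intake, Hypothesis 3 concerns its relationship with postpartum weight loss. The only postpartum analysis in section 10.2 is a regression of weight loss on intake during pregnancy. So six variables have a planned group comparison, and at most four could support a positive claim.

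**3. Chance of at least one false positive if every null is true.** For k independent tests at 0.05 the formula is 1 − 0.95^k:

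- k = 2: 1 − 0.9025 = 9.75%
- k = 4: 1 − 0.8145 = 18.5%

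For correlated tests, two-sided z tests with a common correlation were simulated (400,000 draws). The correlations are assumptions.

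| Tests | Independent | 0.5 | 0.7 | 0.9 |
|---|---|---|---|---|
| 2 (pregnancy intake, two methods) | 9.75% | 9% | 8% | 7% |
| 4 (plus absolute TDEE and SMR) | 18.5% | 16% | 13% | 9% |

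**4. What an alpha split would cost.** At 17/34 and 590 kcal/d, t-test power is 79% at alpha 0.05. It falls to 70% at 0.025 (two tests), 60% at 0.0125 (four) and 50% at 0.00625 (eight).

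**The case against.** The strongest reply is that the plan is less open than section 3.1 suggests. Aim 1 and section 10.1 agree that pregnancy intake is the primary outcome. Section 10.2 treats the two intake methods as corroborating each other: both are expected to be significant, and they are compared by Bland-Altman analysis. If both had to be significant there would be no inflation. The all-null case is also unlikely for intake, because the groups are defined by weight gained (section 8.11) and intake is calculated partly from change in tissue mass (section 8.13). Strict familywise control is not obligatory in a single-arm observational study.

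Much of this stands. It narrows the point to the two intake methods for a reader who goes by Aim 1, and it makes the percentages conditional on nulls that may not hold. But an expectation is not a decision rule, and sections 1 and 3.1 still call the other variables primary. If intake truly differs, the two absolute expenditure tests alone still carry up to 1 − 0.95² = 9.75%.

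A reader might also infer the opposite extreme: eight primary tests, hence 1 − 0.95^8 = 34%, several times a promised 5%. The documents do not support that. Two of the eight have no planned group comparison. For two more, a significant result would contradict the hypothesis. The outcomes are also related by construction: intake is TDEE plus change in energy stores, both methods estimate the same intake, and absolute and adjusted expenditure share data. Even eight tests would give about 25% at correlation 0.5 and 12% at 0.9. Nor does the plan promise a familywise 5%. The 0.05 is a per-test threshold.

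**Conclusion.** The concern holds in a limited form. The definitions of primary in sections 1 and 3.1, in Aim 1 and in section 10.1 conflict, and nothing in section 10.2 governs error across them. That much needs no assumption.

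The size depends on which definition is used. For the four tests that could yield a positive claim, the false-positive chance is about 9% to 18.5%, or 1.9 to 3.7 times nominal. For the two intake methods it is about 7% to 9.75%, or 1.4 to just under 2 times nominal. Both ranges assume that every null in the set is true, and they run from a common correlation of 0.9 down to independence. The documents supply no correlations.

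The adjusted expenditure outcomes have a different weakness: a non-significant p-value would not show that the groups are equal, which is what Hypothesis 2 asserts. This should be corrected because the remedy is cheap. It does not undermine the design.

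**What to change.** - **Primary.** In sections 1, 2.2, 3.1 and 10.1, name one primary outcome: energy intake during pregnancy, from early to late pregnancy testing, by the energy balance method, High versus Normal Gainers, at two-sided 0.05. This is the outcome already powered.
- **Model-based pregnancy intake.** In section 10.2, test it at 0.05 only if the primary test is significant, or state that it is supportive.
- **Absolute TDEE and SMR.** Relabel as secondary.
- **12-month intake.** Relabel as secondary, analysed through the Hypothesis 3 relationship with postpartum weight loss. Do not add a High versus Normal test that the plan does not contain.
- **Adjusted expenditure.** Report the group difference with a 95% confidence interval, as the evidence on Hypothesis 2.

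The cost is an amendment to the text. Sample size and the alpha of the powered test stay as they are, whereas an alpha split would lose power as shown above. The downside is that the relabelled outcomes lose primary status and, if testing is sequential, model-based intake cannot be claimed when the primary test fails.

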3.2. Secondary outcomes

Secondary outcomes include measurement of changes in physical activity and substrate oxidation, determinants of energy intake including fasting concentrations of leptin, total ghrelin, peptide YY, cholecystokinin and determinants of energy expenditure including urinary epinephrine and norepinephrine, and fasting concentrations of T3, T4 and TSH.

4. STUDY POPULATION

4.1. Participants

Up to 75 obese, pregnant women will be recruited for the study. After delivery, the infants born to enrolled mothers will be enrolled to complete 1 study visit before 10 days of life.

4.2. Eligibility Criteria

- Female with singleton, viable pregnancy (confirmed by ultrasound measured $\geq 6,0$ gestation)
- BMI ≥ 30 kg/m² (first study measured weight and height)*
- 18-40 years old
- Medically cleared for participation by primary care obstetrician
- Medically cleared for participation by Medical Investigator
- Willingness to allow the study access to information in your medical record
- Willingness to be notified of incidental findings from study procedures

4.3. Exclusion Criteria

Subjects meeting any of the following criteria are **not** eligible to participate:

Clinical

- Hypertension (i.e. SBP >160 mmHg & DBP >110 mmHg)*
- Diagnosis of diabetes prior to pregnancy
- Hb A1c ≥ 6.5 %*
- Implanted metal objects that render MRI unsafe
- HIV or AIDS (self-reported)
- Severe anemia (hemoglobin <8 g/dL and/or hematocrit <24 %)**

Psychological

- History or current psychotic disorder or diagnosis of a current major depressive episode or bipolar disorder
- Past history of anorexia or bulimia by medical history or patient report (binge eating disorder is not an exclusion) or current eating disorder
- Actively suicidal defined as a value ≥ 2 on the BDI-II question 9*

Medications

- Current use of one or more of the following medications: metformin, systemic steroids, antipsychotic agents (e.g., Abilify, Haldol, Risperdal, Seroquel, Zyprexa), anti-seizure medications or mood stabilizers that would be expected to have a significant impact on body weight (e.g., Depakote, Lamictal, Lithium, Neurontin, Tegretol, Topamax, Keppra), medications for ADHD including amphetamines and methylphenidate
- Continued use of weight loss medication including OTC and dietary supplements for weight loss (e.g., Adipex, Suprenza, Tenuate, Xenical, Alli, conjugated linoleic acid, Hoodia, Green tea extract, Guar gum, HydroxyCut, Sensa, Corti-slim, Chromium, chitosan, Bitter orange)

Other Exclusion Criteria

- Recent history of or currently smoking, drinking alcohol or abusing drugs (prescription or recreational)
- Plans to move out of the study area within the next 2 years or plans to be out of the study area for more than 4 weeks in the next 12 months
- Planned termination of pregnancy
- Unwillingness to avoid pregnancy for 12 months following delivery
- Claustrophobia
- Prior or planned (within 1 year of expected delivery) bariatric surgery
- Participant's unwillingness or inability to commit to a 1 year follow-up
- Recurrent pregnancy during the postpartum period of the study

*Measured during screening

**Abstracted from medical record

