6. SCREENING

Participants will present to Pennington Biomedical to complete a screening visit to assess their eligibility. Participants will provide informed consent prior to the initiation of study procedures. Height, weight, vital signs and HbA1c (by finger stick) will be measured. Medical, obstetrical, medication and psychological history will be reviewed for exclusionary criteria and questionnaires will be administered. A brief discussion (referred to as a Lifestyle Interview) will be used to assess the participant's understanding of the study and willingness to remain in the study in light of potential obstacles to participation, e.g. work schedule, family responsibilities, travel schedule, driving distance to Pennington Biomedical, etc. The participant's medical record will be abstracted to evaluate her gestational age, pregnancy viability and hemoglobin/hematocrit values. The participant's primary care obstetrician will be requested to provide medical clearance for her participation. If inclusion/exclusion criteria are satisfied, the participant is eligible to participate.

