(weeks)	Confirmation of pregnancy-15	13-16	24-27	35-37		+22-25	+48-56
Weight	X	X	X	X		X	X
Height	X						
HbA1c	X						
Prenatal vitamin dispensing/inventory**		X	X	X		X***	
Vital signs (blood pressure, heart rate)	X	X	X	X		X	X
Neck circumference		X	X	X		X	X
Questionnaires	X	X	X	X		X	X
Body composition (BOD POD/SFT)		X	X	X		X	X
Body composition (MRI scan)		X	X	X			X
Energy intake (RFPM)		X		X			X
Accelerometry (Actigraph/Sense Wear)		X		X			X
Doubly Labeled Water (DLW)		X		X			X
Metabolic chamber testing with urine collection		X		X			X
Dinner provided		X		X			X
Breakfast provided		X		X			X
Resting Metabolic Rate (RMR)		X		X			X
Fetal size (3D ultrasound)		X	X	X			
Oral glucose tolerance test							X
Blood collection		X	X	X		X	X
Blood collection for future use*		X	X	X		X	X
Urine collection for future use*		X	X	X		X	X
Placental Biospecimen collection*					X		

*Optional **Subject to participant's needs ***Inventory only

Infant Assessments (Table 2) will be completed at the infant's Delivery visit. The Delivery visit will occur before the infants reach 10 days of life. At the visit, the MomEE participant who is the mother of the infant and signs the minor informed consent will be provided with questionnaires to complete related to the infant. After obtaining written parental informed consent for the infant, weight, recumbent length, head circumference, abdominal circumference and body composition by skinfold thickness and air displacement plethysmography

(PEA POD). Weight, length, and head circumference will be plotted on WHO growth charts. The medical investigator or available nurse practitioner will be called for evaluation of the infant to review any reported adverse events and to determine any signs of jaundice, difficulty breathing, or other obvious congenital malformations. If the medical staff members are unavailable at the time of the visit, follow up may be completed by the medical staff members with the parent/legal guardian of the infant as is deemed necessary. At the MomEE participant mother's 12 month postpartum visit, she will be provided with a Request of Medical Records form to complete for the infant participant so that medical data from the infant's pediatrician's office can be extracted from birth to the end of the infant's first year of life.

Table 2. Infant Assessments	
	Delivery (<10 days old)
Informed Consent (Minor)	X
Length	X
Weight	X
Head Circumference	X
Abdominal Circumference	X
PEAPOD	X
Skinfold Thickness	X
Questionnaires*	X

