9.2. Safety Monitoring/Adverse Events

The following findings would generate a safety alert and study staff should be notified immediately:

1. High Score on the Beck Depression Inventory II
 - Actively suicidal
 - BDI-II question 9 value of 2 or 3 (regardless of BDI-II total score) requires notification of the Principal Investigator (PI) or a designated clinician with appropriate training in mental health assessment. The research staff should wait with the patient until the PI or designated clinician (Pennington psychiatric staff with coordination by the social work department) has the opportunity to assess the participant. The PI or designated clinician should assess the patient for risk of imminent harm to self and contact emergency services if needed. If the PI or designated clinician is not immediately available, notify emergency services according to local standards. Research staff should wait with the participant until emergency services has assumed care.
 - Severe depression
 - BDI-II score of 29-63 (and BDI-II question 9 value of 0 or 1) requires that research staff inform the participant about her elevated score and notify the PI or designated clinician who should assess the patient for safety and/or possible psychiatric referral. If the PI or designated clinician is not immediately available, the participant may leave unattended, but the PI/ designated clinician should contact the participant within 24 hours to assess her for risk of imminent harm and should contact emergency services if needed. The participant should be told to expect such contact from study personnel. The patient's prenatal care provider also should be informed within 2 business days.
 - Moderate depression
 - BDI-II score of 20-28 (and BDI-II question 9 values of 0 or 1) requires that the participant be informed and that it is recommended she see her physician or mental health professional for further evaluation. Participants may be provided with materials on available mental health resources.
2. High Blood pressure
 - If measured blood pressure is $\geq 160/110$, i.e. systolic blood pressure ≥ 160 mm Hg and/or diastolic blood pressure ≥ 110 mm Hg, study staff will call the participant's prenatal care provider immediately and have a Pennington Biomedical physician or nurse practitioner meet with participant and confirm measures. The physician or NP will initiate the action plan.

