 - If measured blood pressure is $\geq 140/90$, i.e. systolic blood pressure ≥ 140 mm Hg and/or diastolic blood pressure ≥ 90 mm Hg, study staff will instruct participants to contact their provider regarding the

PBRC IRB# 13020

elevated measure to arrange appropriate follow-up. Additionally, study staff will notify the prenatal care provider by phone before the end of the study visit.

- At least one blood pressure reading must meet criteria when two readings are taken, and at least two blood pressure readings must meet criteria when three readings are taken.
3. Weight loss from enrollment weight during pregnancy
- Alert values will be weight loss of 6% or greater of enrollment weight for women who were obese at enrollment.
 - For the first weight loss alert, the research staff will notify the patient, discuss her energy balance activities.
 - The patient will be asked to notify prenatal care provider and will be given weight measurement to report to prenatal care provider.
4. Fetal Growth
- Ultrasound alert abnormalities will be determined by physician [name]
5. Infant Growth
- If the infant weight measured is indicative of a $\geq 12\%$ weight loss from birth weight (reported by the parent/legal guardian at the visit), the research staff will notify the infant participants' parent/legal guardian and a referral will be made to the infant's pediatrician with the assistance of the study's medical investigator.
 - If the infant growth safety alert is triggered, the medical investigator or IPU nurse practitioner will be called prior to the conclusion of the study visit for further evaluation of the infant.

An **adverse event** is any untoward medical occurrence including but not limited to:

- Musculoskeletal injury that requires medical attention
- Fetal growth restriction (<5th percentile with abnormal umbilical artery Dopplers)
- Unanticipated untoward medical events

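### The hypertension exclusion needs both pressures above their limits, so a single severely raised pressure at screening (for example 180/100 or 150/115) does not exclude a woman

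*Combined protocol and SAP*

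**What the plan says.** Section 4.3 lists "Hypertension (i.e. SBP >160 mmHg & DBP >110 mmHg" among the clinical exclusions and marks it as measured during screening. Meeting any one exclusion makes a woman ineligible. In the same list, the severe anemia exclusion joins its hemoglobin and hematocrit limits with and/or.

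Section 9.2 has two blood pressure alerts. The upper one applies at "systolic blood pressure ≥ 160 mm Hg and/or diastolic blood pressure ≥ 110 mm Hg"; staff then call the woman's "prenatal care provider immediately and have a Pennington Biomedical physician or nurse practitioner meet with participant and confirm measures". The lower one applies at "systolic blood pressure ≥ 140 mm Hg and/or diastolic blood pressure ≥ 90 mm Hg" and leads to provider notification and follow-up.

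Table 1 in section 7 includes "Vital signs (blood pressure, heart rate" at the screening visit. Section 6 closes with "If inclusion/exclusion criteria are satisfied, the participant is eligible to participate". Section 4.2 adds two clinical requirements to the inclusion list: "Medically cleared for participation by primary care obstetrician" and "Medically cleared for participation by Medical Investigator". Neither carries a blood pressure figure. The opening of section 9 explains that, obesity aside, the criteria were designed to select women at low risk of pregnancy complications.

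**The concern.** With the two limits joined by an ampersand, each does nothing on its own. No systolic value excludes a woman whose diastolic pressure is 110 or lower, and no diastolic value excludes one whose systolic pressure is 160 or lower. Yet section 9.2 treats either value alone as grounds for an immediate call. A pressure that the protocol itself regards as urgent can therefore pass the numeric entry limit, in a study of obese pregnant women whose criteria are meant to select for low risk.

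The stake is participant safety and consistent screening. As written, the decision on a woman with one severely raised pressure rests on individual clinical judgement, because the numeric rule does not reach her.

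**Working it through.** There is no sample size, power or error-rate figure to reproduce. The check applies the written rule to chosen pressures and compares it with two alternatives.

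**Rules**
- W, section 4.3 as written: SBP > 160 and DBP > 110.
- O, ampersand replaced by or, signs unchanged: SBP > 160 or DBP > 110.
- A, the form of the section 9.2 upper alert: SBP ≥ 160 or DBP ≥ 110.

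**Results (is the woman excluded?)**

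| Pressure | W | O | A |
|---|---|---|---|
| 161/111 | yes | yes | yes |
| 180/100 | no (100 is not above 110) | yes | yes |
| 200/110 | no (110 is not above 110) | yes | yes |
| 150/115 | no (150 is not above 160) | yes | yes |
| 160/120 | no (160 is not above 160) | yes | yes |
| 160/110 | no (neither is above its limit) | no | yes |
| 155/105 | no | no | no |

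**Reading the table**
1. Moving from W to O brings in 180/100, 200/110, 150/115 and 160/120. This is the substantive gap, and it comes from the ampersand alone.
2. Moving from O to A changes only pairs with a pressure exactly on its limit and neither above it. In the table that is 160/110.
3. Rule A only adds exclusions. If SBP > 160 and DBP > 110, then SBP ≥ 160 is already true, so everyone excluded today stays excluded. A woman at 155/105 stays eligible.

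**Comparison within the protocol.** Both alerts in section 9.2 and the anemia line in section 4.3 use and/or. The hypertension exclusion is the only blood pressure rule written with an ampersand and strict signs. Nothing elsewhere redefines it.

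**The case against.** **Clinical clearance already covers these women.** Both clearances are inclusion criteria, so the section 6 eligibility sentence already takes them in. A woman at 180/100 cannot enter until her obstetrician and the Medical Investigator both agree. This stands and is the main reason the harm is limited. But neither clearance states a pressure, so neither repairs the numeric rule.

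**The section 9.2 alert probably applies at screening.** It refers to measured blood pressure with no visit limit, whereas the weight-loss alert is tied to enrollment weight. The same alert list covers the BDI-II suicidality item, which is also given at screening. If so, the prenatal provider would hear of the reading at once. This is a reasonable inference, but an alert prompts clinical action and does not exclude. The 140/90 alert, for instance, has no matching exclusion.

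**The ampersand may be loose drafting for and/or.** Quite possibly, given the wording used elsewhere. That is a reason to correct it, since staff applying the text literally would reach a different answer from the one intended.

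**Stronger readings that the documents do not support.** A reader might infer from 161/111 being excluded and 180/100 not that the rule fails to rank women by pressure. It does not fail in that sense. If a pair is excluded, any pair at least as high on both pressures is excluded too. Neither of 161/111 and 180/100 is at least as high as the other on both components, and the amended rule gives contrasts of the same kind: it excludes 160/70 and admits 159/109. A reader might also infer that such women would be enrolled; with two clearances required, the documents do not show that. Nor is the treatment of exactly 160/110 an error of equal weight: an entry limit need not equal an alert limit, so that is only a matter of alignment.

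**Conclusion.** The point holds in a limited form. As written, one severely raised pressure alone never triggers the only numeric blood pressure limit for entry. That does not fit the either-value form of the section 9.2 alerts or the low-risk purpose stated in section 9.

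Severity is minor. No endpoint, estimate, power figure or analysis is affected, and the documents give no screening blood pressure distribution from which to count the women concerned. The conclusion assumes that the ampersand is applied literally. The view that harm is limited rests on both clearances being exercised as required and, to a lesser extent, on the alert operating at screening.

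**What to change.** Amend the hypertension line in section 4.3 to read: SBP ≥160 mmHg and/or DBP ≥110 mmHg. Replacing the ampersand with and/or closes the gap; the inclusive signs simply match the section 9.2 boundary. If the sponsor prefers to keep the strict signs, the and/or change alone deals with the substantive issue.

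No other section needs to change. The cost is one line in a protocol amendment and possibly a few more screen failures.
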